5.2 Trial Treatments

The treatments to be used in this trial is outlined below in Table 2

Table 2 Trial Treatments

Drug	Dose/Potency	Dose Frequency	Route of Administration	Regimen/Treatment Period	Use
ADV/HSV-tk	5 x 10 ¹¹ vp in 2-mL volume	Once	Intratumorally	Day 0	Experimental
Valacyclovir	2 g	t.i.d. for 14 days	Orally	Day 1 - Day 15	Experimental
SBRT*	30 Gy	6 Gy X 5 fractions over 14 days	-	Day 2 - Day 16	Experimental

Drug	Dose/Potency	Dose Frequency	Route of Administration	Regimen/Treatment Period	Use
Pembrolizumab**	200 mg	Q3W	IV infusion	Day 1 of each 3-week cycle	Experimental

vp = viral particles; t.i.d. = three times daily; Q3W = every 3 weeks; IV = intravenous.

*Primary breast tumors will be treated with three-dimensional RT (short course of 5–8 fractions).

**Pembrolizumab will continue until disease progression, unacceptable toxicity, or up to 24 months (35 cycles) in subjects without disease progression. All subjects who stop pembrolizumab treatment with complete response may be eligible for up to an additional 12 months (17 cycles) of pembrolizumab treatment if they progress after stopping pembrolizumab from the initial treatment phase. The subject must meet the conditions outlined in Section 5.2.3.

ADV/HSV-tk

The tumor will be identified by positron emission tomography (PET)/CT by the radiation oncologist. ADV/HSV-tk will be administered intratumorally as a single injection using a 21-gauge needle. For nodal, lung, and liver lesions, ADV/HSV-tk will be administered after fiducial placement for SBRT. For primary lung tumors, ADV/HSV-tk will be administered under endobronchial ultrasound (EBUS) guidance. In cases where the tumor cannot be accessed by EBUS, a CT-guided injection will be performed. For primary breast tumors, ADV/HSV-tk will be administered under ultrasound guidance. For liver and lung metastatic lesions, ultrasound or CT-guided injection of ADV/HSV-tk will be performed. EBUS will be performed with the patient under sedation. Patients will be monitored until the sedation has worn off. For CT-guided injections, local anesthesia will be used and patients will be monitored for several hours after the procedure.

SBRT

Primary lung tumors and metastatic lesions (breast and lung) will be treated with SBRT (6 Gy X 5 fractions over 2 weeks). Primary breast tumors will be treated with three-dimensional (3D) RT (short course of 5–8 fractions over 2 weeks). Tumor target will be decided by PET/CT scan. For the planned dosing regimen, SBRT simulation will be done before treatment. For subjects with multiple tumors, the largest tumor will be selected. Sedation is not necessary for SBRT.

5.2.1 Dose Selection/Modification

5.2.1.1 Dose Selection

The rationale for selection of doses to be used in this trial is provided in Section 4.0 – Background and Rationale.

5.2.1.2 Dose Modification

Pembrolizumab: AEs (both non-serious and serious) associated with pembrolizumab exposure may represent an immunologic etiology. These AEs may occur shortly after the first dose or several months after the last treatment dose. Pembrolizumab must be withheld for drug-related toxicities and severe or life-threatening AEs as per Table 3 below. See Section 5.4 for supportive care guidelines, including use of corticosteroids.

Table 3 Dose Modification Guidelines for Pembrolizumab-Related AEs

Toxicity	Hold Treatment For Grade	Timing for Restarting Treatment	Treatment Discontinuation
Diarrhea/Colitis	2-3	Toxicity resolves to Grade 0-1	Toxicity does not resolve within 12 weeks of last dose or inability to reduce corticosteroid to 10 mg or less of prednisone or equivalent per day within 12 weeks
	4	Permanently discontinue	Permanently discontinue
Increased AST, ALT, or Bilirubin	2	Toxicity resolves to Grade 0-1	Toxicity does not resolve within 12 weeks of last dose
	3-4	Permanently discontinue (see exception below) ^a	Permanently discontinue
Type 1 Diabetes Mellitus (T1DM; if new onset) or Hyperglycemia	T1DM or 3-4	Hold pembrolizumab for new onset T1DM or Grade 3-4 hyperglycemia associated with evidence of beta cell failure	Resume pembrolizumab when patients are clinically and metabolically stable
Hypophysitis	2-4	Toxicity resolves to Grade 0-1. Therapy with pembrolizumab can be continued while endocrine replacement therapy is instituted	Toxicity does not resolve within 12 weeks of last dose or inability to reduce corticosteroid to 10 mg or less of prednisone or equivalent per day within 12 weeks
Hyperthyroidism	3	Toxicity resolves to Grade 0-1	Toxicity does not resolve within 12 weeks of last dose or inability to reduce corticosteroid to 10 mg or less of prednisone or equivalent per day within 12 weeks
	4	Permanently discontinue	Permanently discontinue
Hypothyroidism		Therapy with pembrolizumab can be continued while thyroid replacement therapy is instituted	Therapy with pembrolizumab can be continued while thyroid replacement therapy is instituted
Infusion Reaction	2 ^b	Toxicity resolves to Grade 0-1	Permanently discontinue if toxicity develops despite adequate premedication
	3-4	Permanently discontinue	Permanently discontinue
Pneumonitis	2	Toxicity resolves to Grade 0-1	Toxicity does not resolve within 12 weeks of last dose or inability to reduce corticosteroid to 10 mg or less of prednisone or equivalent per day within 12 weeks
	3-4	Permanently discontinue	Permanently discontinue
Renal Failure or Nephritis	2	Toxicity resolves to Grade 0-1	Toxicity does not resolve within 12 weeks of last dose or inability to reduce corticosteroid to 10 mg or less of prednisone or equivalent per day within 12 weeks
	3-4	Permanently discontinue	Permanently discontinue
All Other Drug-Related Toxicity ^c	3 or Severe	Toxicity resolves to Grade 0-1	Toxicity does not resolve within 12 weeks of last dose or inability to reduce corticosteroid to 10 mg or less of prednisone or equivalent per day within 12 weeks
	4	Permanently discontinue	Permanently discontinue

Toxicity	Hold Treatment For Grade	Timing for Restarting Treatment	Treatment Discontinuation

Note: Permanently discontinue for any severe or Grade 3 drug-related AE that recurs or any life-threatening event.
 
^a For patients with liver metastasis who begin treatment with Grade 2 AST or ALT, if AST or ALT increases by greater than or equal to 50% relative to baseline and lasts for at least 1 week then patients should be discontinued from treatment.
 
^b If symptoms resolve within one hour of stopping drug infusion, the infusion may be restarted at 50% of the original infusion rate (e.g., from 100 mL/hr to 50 mL/hr). Otherwise, dosing will be held until symptoms resolve and the subject should be premedicated for the next scheduled dose. Refer to Table 4 – Infusion Treatment Guidelines for further management details.
 
^c Patients with intolerable or persistent Grade 2 drug-related AE may hold study medication at physician discretion. Permanently discontinue study drug for persistent Grade 2 adverse reactions for which treatment with study drug has been held that do not recover to Grade 0-1 within 12 weeks of the last dose.
			

ADV/HSV-tk oncolytic virus therapy: Significant toxicity has not been observed with the administration of ADV/HSV-tk oncolytic virus therapy alone or in combination with RT or chemotherapy in previous clinical trials.^{71, 73, 75, 76} Fever may occur due to the local inflammatory and immune response to ADV-tk, which will be treated with acetaminophen as necessary. If local inflammation is extensive or infection develops, valacyclovir will be stopped and antibiotics and/or anti-inflammatory therapy will be given as appropriate.

In both the TNBC and NSCLC cohorts, ADV/HSV-tk dose will be de-escalated to 5×10^9 vp if unacceptable toxicity occurs with the planned dose of ADV/HSV-tk. If toxicity occurs with this dose modification, the dose will be further de-escalated to 5×10^6 vp.

Dosing interruptions for pembrolizumab and SBRT/3D RT are permitted in the case of medical/surgical events or logistical reasons not related to study therapy (e.g., elective surgery, unrelated medical events, patient vacation, and/or holidays). Subjects should be placed back on study therapy within 3 weeks of the scheduled interruption, unless otherwise discussed with the Sponsor. The reason for interruption should be documented in the patient's study record. Patients whose treatment is interrupted or permanently discontinued due to an AE including abnormal laboratory value must be followed at least once a week for 4 weeks and subsequently at 4-week intervals until resolution or stabilization of the event, whichever comes first. Dose interruptions should be reported on the appropriate Dosage Administration case report form (CRF). The maximum time allowed for toxicity-related treatment interruption is 21 days (3 weeks) from the intended dosing day. If interruption is > 3 weeks, the patient must be discontinued from the study treatment. However, the patient will continue to be followed for toxicity.

Valacyclovir: For patients with serum creatinine level of $1.6\text{--}2.0 \times \text{ULN}$, valacyclovir dose will be reduced 50% (i.e., 1 g t.i.d.).

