Serum total bilirubin	≤1.0 X ULN (Subjects with known Gilbert's disease who have serum bilirubin level ≤3 X ULN may be enrolled)
Aspartate transaminase (AST) and Alanine transaminase (ALT)	≤2.5 X ULN with normal alkaline phosphatase (≤5 X ULN for subjects with liver metastases) OR ≤1.5 X ULN in conjunction with alkaline phosphatase >2.5 X ULN
Albumin	≥2.5 mg/dL
Coagulation	
International normalized ratio (INR) or prothrombin time (PT)	≤1.5 X ULN unless subject is receiving anticoagulant therapy as long as PT or aPTT is within therapeutic range of intended use of anticoagulants
Activated partial thromboplastin time (aPTT)	≤1.5 X ULN unless subject is receiving anticoagulant therapy as long as PT or aPTT is within therapeutic range of intended use of anticoagulants
^a CrCl should be calculated per institutional standard.	

8. Life expectancy ≥ 6 months.
9. ≥ 4 weeks since any major surgery.
10. A 2-week washout period post any prior systemic anticancer therapy, RT, targeted anticancer therapy or mAb, and/or investigational therapy is required prior to trial entry. Subject should be recovered (i.e., ≤ Grade 1 or at baseline) from AEs due to a previously administered therapy.
 - Note: Subjects with ≤ Grade 2 neuropathy are an exception to this criterion and may qualify for the study.
11. Female subjects of childbearing potential should have a negative serum pregnancy (β-human chorionic gonadotropin [β-HCG]) within 7 days prior to receiving the first dose of the trial treatment and should not be lactating.
12. Female subjects of childbearing potential (Section 5.5.2) must be willing to use an adequate method of contraception as outlined in Section 5.5.2 – Contraception, for the course of the study through 120 days after the last dose of study medication.

Note: Abstinence is acceptable if this is the usual lifestyle and preferred contraception for the subject.
13. Male subjects of childbearing potential (Section 5.5.2) must agree to use an adequate method of contraception as outlined in Section 5.5.2 – Contraception, starting with the first dose of study therapy through 120 days after the last dose of study therapy.

Note: Abstinence is acceptable if this is the usual lifestyle and preferred contraception for the subject.

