- When symptoms improve to Grade 1 or less, steroid taper should be started and continued over no less than 4 weeks.

- **T1DM if new onset (including diabetic ketoacidosis) or \geq Grade 3 hyperglycemia if associated with ketosis (ketonuria) or metabolic acidosis**

- For **T1DM** or **Grade 3–4 Hyperglycemia**
 - Insulin replacement therapy is recommended for T1DM and for Grade 3–4 hyperglycemia associated with metabolic acidosis or ketonuria.
 - Evaluate patients with serum glucose and a metabolic panel, urine ketones, glycosylated hemoglobin, and C-peptide.

- **Hypophysitis:**

- For **Grade 2 events**, treat with corticosteroids. When symptoms improve to Grade 1 or less, steroid taper should be started and continued over no less than 4 weeks. Replacement of appropriate hormones may be required as the steroid dose is tapered.
- For **Grade 3–4 events**, treat with an initial dose of IV corticosteroids followed by oral corticosteroids. When symptoms improve to Grade 1 or less, steroid taper should be started and continued over no less than 4 weeks. Replacement of appropriate hormones may be required as the steroid dose is tapered.

- **Hyperthyroidism or Hypothyroidism:**

Thyroid disorders can occur at any time during treatment. Monitor patients for changes in thyroid function (at the start of treatment, periodically during treatment, and as indicated based on clinical evaluation) and for clinical signs and symptoms of thyroid disorders.

- **Grade 2** hyperthyroidism events (and **Grade 2–4** hypothyroidism):
 - In hyperthyroidism, non-selective beta-blockers (e.g., propranolol) are suggested as initial therapy.
 - In hypothyroidism, thyroid hormone replacement therapy with levothyroxine or liothyronine is indicated per standard of care.
- **Grade 3-4** hyperthyroidism
 - Treat with an initial dose of IV corticosteroid followed by oral corticosteroids. When symptoms improve to Grade 1 or less, steroid taper should be started and continued over no less than 4 weeks. Replacement of appropriate hormones may be required as the steroid dose is tapered.

- **Hepatic:**

- For **Grade 2** events, monitor liver function tests more frequently until returned to baseline values (consider weekly).
 - Treat with IV or oral corticosteroids
- For **Grade 3–4** events, treat with IV corticosteroids for 24 to 48 hours.
- When symptoms improve to Grade 1 or less, a steroid taper should be started and continued over no less than 4 weeks.

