7.2 Assessing and Recording Adverse Events

An AE is defined as any untoward medical occurrence in a patient or clinical investigation subject administered a pharmaceutical product and which does not necessarily have to have a causal relationship with this treatment. An AE can, therefore, be any unfavorable and unintended sign (e.g., abnormal laboratory finding), symptom, or disease temporally associated with the use of a medicinal product or protocol-specified procedure, whether or not considered related to the medicinal product or protocol-specified procedure. Any worsening (i.e., any clinically significant adverse change in frequency and/or intensity) of a preexisting condition that is temporally associated with the study treatment is also an AE. Progression of the cancer under study is not considered an AE.

All AEs that occur after informed consent form signing must be reported by the investigator if they cause the subject to be excluded from the trial or are the result of a protocol-specified intervention, including but not limited to washout or discontinuation of usual therapy, diet, placebo treatment, or a procedure.

From the time of informed consent signing through 30 days following cessation of treatment, all AEs must be reported by the investigator. AE reporting will be performed according to 21 CFR 312.32. AEs will be recorded at each examination on the Adverse Event CRFs/worksheets. AEs (including lab abnormalities that constitute AEs) should be described using a diagnosis whenever possible, rather than individual underlying signs and symptoms. When a clear diagnosis cannot be identified, each sign or symptom should be reported as a separate AE. Conditions that were already present at the time of informed consent should be recorded in the Medical History page of the subject's CRF. The reporting timeframe for AEs meeting any serious criteria is described in section 7.2.3.1. The investigator will make every attempt to follow all subjects with non-SAEs for outcome.

AEs will not be collected for subjects during the prescreening period as long as that subject has not undergone any protocol-specified procedure or intervention. If the subject requires a blood draw, fresh tumor biopsy etc., the subject is first required to provide consent to the main study and AEs will be captured according to guidelines for standard AE reporting.

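### For patients with liver metastases who begin at Grade 2 AST/ALT, Table 3's liver lines, footnote a, the 21-day limit and Section 5.6 give conflicting hold, restart and stop instructions

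*Combined protocol and SAP*

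**What the plan says.** - **Entry (5.1.2, Table 1).** The AST/ALT limit is 2.5 x ULN with normal alkaline phosphatase, relaxed to "≤5 X ULN for subjects with liver metastases".
- **Scope (5.2.1.2).** "Pembrolizumab must be withheld for drug-related toxicities and severe or life-threatening AEs as per Table 3 below". Under Section 7.2, an adverse event includes "Any worsening (i.e., any clinically significant adverse change in frequency and/or intensity) of a preexisting condition that is temporally associated with the study treatment".
- **Table 3, liver, Grade 2.** Hold; restart at Grade 0-1; discontinue if "Toxicity does not resolve within 12 weeks of last dose". No footnote is attached.
- **Table 3, liver, Grade 3-4.** These grades are in the hold column. The restart column reads "Permanently discontinue (see exception below" and points to footnote a.
- **Footnote a.** It begins "For patients with liver metastasis who begin treatment with Grade 2 AST or ALT". Such patients are to be discontinued if AST or ALT rises by 50% or more over baseline for at least 1 week.
- **General note to Table 3.** A recurrent Grade 3 drug-related event, or any life-threatening event, ends treatment.
- **Later text of 5.2.1.2.** A toxicity-related interruption may last at most 21 days from the intended dosing day. Beyond that, study treatment stops.
- **Section 5.6.** A dose interruption over 21 days, any Grade 4 or greater event, and a Grade 3 immune-mediated complication each require discontinuation. None has a liver-metastasis exception.

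**The concern.** The protocol knowingly admits patients whose transaminases are already at Grade 2, and adapts its stopping rule to their own baseline on only one of the two liver lines. On the other line the reference is absolute grade, so a held patient must improve beyond the entry state before restarting. Different passages also give different time limits and different triggers for a permanent stop.

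Two investigators applying the text in good faith could hold, continue or stop pembrolizumab for the same laboratory value. That bears on patient safety and on pembrolizumab exposure. It also bears on the frequencies of dose interruption and toxicity-related discontinuation that Section 8.1 says will be reported.

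**Working it through.** The plan gives no figure to reproduce on this point. The check is of rule logic, with arithmetic to see whether the conflicts can arise within the eligible range.

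**Inputs.** Entry limit with liver metastases: 5 x ULN (Table 1). Footnote a threshold: 50% over baseline for 1 week. Time limits: 12 weeks from last dose (Table 3) and 21 days from the intended dosing day (5.2.1.2). Dosing interval: 3 weeks (Table 2). Section 12.2 names CTCAE v4.03, but the documents do not print the AST/ALT cut-points. Two assumptions are therefore needed, in x ULN: *T*, the Grade 2/3 boundary, varied from 4 to 6; and *L*, the Grade 1/2 boundary, varied from 2.5 to 3.5. Let *b* be the baseline.

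**1. Restart on the Grade 2 line.** A patient entering at Grade 2 has *b* > *L*, and restart needs a value of *L* or below. The required fall below the patient's own baseline is (*b* − *L*)/*b*. At *b* = 4.0 this is 37.5% for *L* = 2.5, 25% for *L* = 3.0 and 12.5% for *L* = 3.5. It is positive for any *L*, because *b* is Grade 2 by definition.

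**2. Time limit.** If the hold begins at a scheduled dose, the intended dosing day is day 21 after the last dose. The 21-day limit then expires on day 21 + 21 = 42. Table 3's limit expires on day 12 × 7 = 84. From day 42 to day 84, Table 3 still allows recovery, while 5.2.1.2 and 5.6 have already ended treatment. This clash is not specific to the liver, but it matters particularly where the restart target lies below the entry value.

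**3. Grade 3 rises spared by footnote a.** A Grade 3 value with a rise under 50% satisfies *T* < value < 1.5*b*, which requires *b* > *T*/1.5.

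| Assumed *T* | Band exists for *b* above |
|---|---|
| 4.0 | 2.67 |
| 4.5 | 3.00 |
| 5.0 | 3.33 |
| 5.5 | 3.67 |
| 6.0 | 4.00 |

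All are below the 5 x ULN entry limit. With *T* = 5:

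| *b* | Rise that reaches 5.0 | 1.5*b* | Grade 3 band with rise under 50% |
|---|---|---|---|
| 3.1 | 61.3% | 4.65 | none |
| 3.3 | 51.5% | 4.95 | none |
| 3.4 | 47.1% | 5.10 | 5.0 to 5.1 |
| 4.0 | 25.0% | 6.00 | 5.0 to 6.0 |
| 4.5 | 11.1% | 6.75 | 5.0 to 6.75 |

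A rise of 50% or more that lasts under 1 week is also spared. For a spared value, footnote a waives the permanent stop but says nothing on hold or restart. If the event is judged immune-mediated, 5.6 requires discontinuation regardless.

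**4. Rises of 50% or more that stay in Grade 2.** These need 1.5*b* ≤ *T* with *b* > *L*, so they are possible only when 1.5*L* < *T*. That means *T* above 3.75, 4.5 or 5.25 for *L* = 2.5, 3.0 or 3.5. With *L* = 3.0 and *T* = 5, a baseline of 3.1 rising 50% reaches 4.65, still Grade 2. If this is a drug-related event lasting a week, footnote a's wording says discontinue and the Grade 2 line says hold and restart.

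**5. One patient, two values** (*L* = 3.0, *T* = 5, *b* = 4.0). At 4.4 (+10%, Grade 2), if clinically significant and drug-related: hold, restart only at 3.0 or below, otherwise stop. At 5.8 (+45%, Grade 3): no permanent stop under footnote a, restart rule unstated, stop under 5.6 if immune-mediated.

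**The case against.** The strongest defence is that footnote a is a specific rule for a named population. Its wording is not limited to Grade 3, so it could be taken to replace both liver lines for these patients. That would remove the overlap in step 4. But the marker is on one line only, and nothing says that the Grade 2 line is displaced.

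Several stronger readings are tempting and do not hold:

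- A reader might infer that a Grade 3 rise leads to neither hold nor stop. Grade 3-4 is in the hold column, and the exception qualifies only the permanent stop. The accurate statement is that hold and restart are unstated.
- A reader might infer that the larger rise is always treated more leniently. Footnote a itself ends treatment for a 50% rise lasting a week; at *T* = 5, a Grade 3 value from a baseline of 3.1 or 3.3 already exceeds 50%. Section 5.6 and the recurrence note can also end treatment.
- A reader might infer that an unchanged Grade 2 baseline, or any small fluctuation, triggers a hold. Table 3 concerns drug-related toxicity, and Section 7.2 requires clinically significant worsening.
- Section 5.4.1's "monitor liver function tests more frequently until returned to baseline values" might look like another restart criterion. It governs monitoring frequency, and that section refers back to 5.2.1.2 for dose modification.
- Inclusion criterion 4 might suggest that liver metastases will be common. It requires a visceral metastatic lesion, not a hepatic one.

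These limits narrow the point. They leave the missing baseline reference on the Grade 2 line, the two time limits, and the mismatch between footnote a and 5.6.

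**Conclusion.** The concern holds as a conflict between rules for patients with liver metastases who begin at Grade 2 AST/ALT. A qualifying Grade 2 event can restart only at a grade better than at entry. Recovery time is 12 weeks or 21 days depending on the passage (day 84 or day 42 after the last dose, on a 3-week schedule). A Grade 3 rise may be spared by footnote a yet require discontinuation under 5.6.

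The restart problem and the time-limit conflict do not depend on the cut-points. The spared Grade 3 band exists for every assumed Grade 2/3 boundary from 4 to 6 x ULN. The overlap in step 4 also depends on the Grade 1/2 boundary and on reading footnote a as applying within Grade 2.

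The documents do not say how many of the 57 patients would be affected, so the effect on exposure and on reported discontinuation rates cannot be quantified. They do not support a claim that the rules systematically favour larger rises. No sample-size or error-rate figure is involved. The change should be made because the protocol expressly admits these patients.

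**What to change.** Reconcile five items for patients with liver metastases who begin at Grade 2 AST/ALT: the Grade 2 liver line, the Grade 3-4 liver line with footnote a, the 12-week limit, the 21-day limit in 5.2.1.2 and 5.6, and the Section 5.6 rule on Grade 3 immune-mediated complications. State on both liver lines whether absolute grade or the patient's own baseline governs hold, restart and discontinuation, and which passage prevails where they differ. The sponsor's clinicians decide the rule and thresholds; this review proposes none.

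The cost is a wording amendment to Table 3, 5.2.1.2 and 5.6, with no added tests, visits or patients.

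### Pembrolizumab stopping rules conflict: the 21-day cap and the Grade 3 stop in 5.6 contradict the 12-week and restart provisions of Table 3

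*Combined protocol and SAP*

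**What the plan says.** **Section 5.2.1.2, introduction to Table 3.** "Pembrolizumab must be withheld for drug-related toxicities and severe or life-threatening AEs as per Table 3 below".

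**Table 3.** The usual condition for permanent discontinuation begins: "Toxicity does not resolve within 12 weeks of last dose or inability to reduce corticosteroid to 10 mg or less of prednisone or equivalent". The 12-week limit appears in seven of ten rows: diarrhea/colitis, hepatic, hypophysitis, hyperthyroidism, pneumonitis, renal, and other drug-related toxicity. Footnote c applies it to held, persistent Grade 2 reactions as well. The row for type 1 diabetes (T1DM) and hyperglycemia has no time limit and says: "Resume pembrolizumab when patients are clinically and metabolically stable". The hypothyroidism row gives no grade: "Therapy with pembrolizumab can be continued while thyroid replacement therapy is instituted". A note to the table adds: "Permanently discontinue for any severe or Grade 3 drug-related AE that recurs or any life-threatening event".

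**Section 5.2.1.2, text after Table 3.** "The maximum time allowed for toxicity-related treatment interruption is 21 days (3 weeks) from the intended dosing day". It continues: "If interruption is > 3 weeks, the patient must be discontinued from the study treatment". Earlier in the same paragraph, for interruptions unrelated to study therapy, there is a softer rule: "Subjects should be placed back on study therapy within 3 weeks of the scheduled interruption, unless otherwise discussed with the Sponsor".

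**Section 5.6.** This lists reasons for which a subject must be discontinued. They include an interruption longer than 21 days, any adverse event of Grade 4 or above, and an immune-mediated complication of Grade 3 or 4. None of these entries carries an exception.

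**The concern.** Two investigators who both follow the protocol could treat the same event in opposite ways. One who applies 5.6 ends treatment that Table 3 would allow to restart. One who applies Table 3 re-exposes a patient whom 5.6 says must stop. Both sets of rules govern safety, and no sentence gives either precedence.

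The statistical consequence is narrower. Section 8.1 plans to report how often dosing is interrupted and how often treatment is discontinued for toxicity. If the discontinuation rule depends on which section was consulted, that frequency reflects the choice of section as well as the regimen's toxicity.

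**Working it through.** **Step 1: put both time limits on one clock.** They start from different days, so 21 days and 12 weeks cannot be compared directly.

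Inputs:
- pembrolizumab interval of 21 days, ± 1 day (5.2.2)
- cap of 21 days from the intended dosing day (text of 5.2.1.2)
- Table 3 limit of 12 weeks from the last dose

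Arithmetic, in days after the last dose:
- Cap: interval + cap = 21 + 21 = day 42.
- Table 3: 12 × 7 = day 84.
- Gap: 84 − 42 = 42 days.

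Toxicity that resolves between about day 43 and day 84 therefore means mandatory discontinuation under the cap and permitted restart under Table 3. The ± 1 day window moves the first limit by a day only. Section 5.6 does not say where its 21 days begin. I have used the 5.2.1.2 starting point; counted from the last dose, the gap would be 84 − 21 = 63 days.

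This conflict also reaches Grade 2 holds (colitis, hepatic, pneumonitis, renal), which the Grade 3 rule in 5.6 does not touch.

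**Step 2: compare Table 3 with the Grade 3 immune-mediated rule in 5.6.**

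| Table 3 row | Table 3 at Grade 3 | Against 5.6 |
|---|---|---|
| T1DM / hyperglycemia | resume when stable | conflict |
| Hypophysitis | restart, or continue with hormone replacement | conflict |
| Hyperthyroidism | restart after recovery | conflict |
| Hypothyroidism | continue, no grade stated | conflict |
| Diarrhea/colitis | restart after recovery | conflict if immune-mediated |
| Other drug-related toxicity | restart after recovery | conflict if immune-mediated |
| Hepatic | stop (one footnoted exception) | agree |
| Infusion reaction | stop | agree |
| Pneumonitis | stop | agree |
| Renal | stop | agree |

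That is 4 conflicts + 2 partial conflicts + 4 agreements = 10 rows.

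Neither section defines an immune-mediated complication. Elsewhere the protocol treats the four conflicting conditions as immune-related: Section 4.1 counts hypophysitis and thyroid disorders among immune-mediated events, and 5.4.1 places new-onset diabetes and severe hyperglycemia among events of possible immunologic origin.

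Restart after a first Grade 3 event looks intended in Table 3, because its note orders a permanent stop only when such an event recurs.

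**Step 3: Grade 4.** Table 3 permits restart or continuation after Grade 4 hypophysitis, resumption after Grade 4 hyperglycemia and, having no grade limit, continuation in Grade 4 hypothyroidism. All three conflict with the Grade 4 entry in 5.6. If the event is life-threatening, they also conflict with Table 3's own note.

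**The case against.** The best defence is that the rules can be applied together, with the strictest always winning. Most Table 3 provisions are permissions or conditions, so an investigator who always stops breaches almost nothing. This has some force, but it does not dispose of the point. Always stopping contradicts the directive to resume in the T1DM/hyperglycemia row, makes the immune-mediated Grade 3 restart provisions void, and leaves the 12-week resolution criterion with no function for a held patient. Section 5.2.1.2 also tells investigators to withhold drug according to Table 3, and 5.4.1 sends them to that section for dose modification.

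A second defence is the rechallenge entry in Table 6 (7.2.4). Re-exposure after a serious event possibly caused by the drug, or where re-exposure carries significant added risk, needs the sponsor's prior approval. That softens the safety risk. However, it refers back to the same dose modification guidelines, does not settle the 21-day cap, and does not amend 5.6.

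A third is that contact with the sponsor can lift the cap. That exception is attached to interruptions unrelated to study therapy; the toxicity cap has none.

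Two objections stand. The stricter rule in 5.6 could be deliberate for a new combination still in a safety run-in, so the documents do not show that Table 3 ought to prevail. Diarrhea/colitis is only a partial conflict, because 5.4.1 recognises that severe diarrhea may turn out not to be colitis.

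**Conclusion.** The contradiction is real and should be fixed. It has three parts: 42 days' difference in the permitted interruption, four full and two partial row conflicts at Grade 3, and three cells that disagree with the Grade 4 rule. The 42 days assumes three-weekly dosing and that 5.6 counts from the intended dosing day.

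Few patients are likely to be affected at Grade 3. In the monotherapy trials summarised in 4.1.1.4.5, drug-related serious colitis ran at 0.3–0.9%, and hypophysitis, hyperthyroidism and hypothyroidism at 0.2–0.3% each. Serious is only a proxy for Grade 3, and the documents give no rates for this combination.

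Four stronger readings are tempting but unsupported:
- **A gap of 3 against 12 weeks.** On a common clock the text of 5.2.1.2 allows 6 weeks, not 3.
- **A stated chance that the conflict will arise among the 57 patients.** The serious-event proxy is too weak for that, and there are no time-to-resolution data from which to count patients in the day 43–84 window.
- **Bias in ORR, DoR or PFS.** Patients who stop for reasons other than progression continue to be imaged (5.6 and 7.1.5.1.2), and the documents do not show how early stopping would alter response.
- **Documented differences between sites.** The documents do not give the number of sites; the ambiguity faces any two investigators.

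**What to change.** State one governing rule for pembrolizumab toxicity. Which one is the sponsor's clinical decision.

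**If Table 3 governs:**
- In the text of 5.2.1.2 and the 5.6 interruption entry, exempt pembrolizumab toxicity holds that are within Table 3 limits.
- Keep the 21-day cap for toxicity-related interruptions of SBRT or 3D RT, which Table 3 does not cover.
- Keep the sponsor-discussion exception for interruptions unrelated to therapy, and add it to the 5.6 entry.
- In the 5.6 entry on Grade 3 immune-mediated complications, except events for which Table 3 permits restart or continuation.
- Make the Grade 4 hypophysitis, hyperglycemia and hypothyroidism cells agree with the Grade 4 and life-threatening-event rules.

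**If 5.6 governs:**
- Change the 12-week cells and footnote c to the 21-day limit.
- Change the Grade 3 restart cells, the resume instruction and the ungraded hypothyroidism cell to match 5.6.

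Under either choice, use the same rule to classify toxicity-related discontinuation in 8.1.

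The cost is amendment wording and a notice to investigators, with no extra patients or procedures. Choosing Table 3 would permit more re-exposure than 5.6 now does, so it should be agreed as a safety decision and not treated as an editorial correction.
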